13.2 Consent

W-C19 Screener Consent Form

Check if VA related

a) Describe the informed consent process. Include the following.

- Who is obtaining consent? (The person obtaining consent must be knowledgeable about the study.)
- When and where will consent be obtained?
- How much time will be devoted to consent discussion?
- Will these periods provide sufficient opportunity for the participant to consider whether or not to participate and sign the written consent?
- What steps are you taking to minimize the possibility of coercion and undue influence?
- If consent relates to children and if you have a reason for only one parent signing, provide that rationale for IRB consideration.

(i)Study staff will be obtaining the consent via online questionnaire (Qualtrics or REDCap). (ii)This consent will be at the beginning of the screening questionnaire (Qualtrics or REDCap). Since consent is obtained online, it can be obtained at any location of the participants choosing. (ii)There is no time limit- each respondent can take much time as they want to read through the consent. Reading consent is anticipated to not take more than five minutes. (iv)Since consent is obtained online, the participant may take as much time as they wish to consider whether or not to participate and proceed with the screener. The online survey platform can obtain electronic signatures, and participants can sign the online consent by mouse, finger, or stylus. (v)No incentive for form of coercion is present for the screening process. The study is voluntary; Participants are informed that they can withdraw or choose not to participate at any time. There is no payment for going through the screener. (vi)N/A.

b) What is the Procedure to assess understanding of the information contained in the consent? How will the information be provided to participants if they do not understand English or if they have a hearing impairment? See HRPP Chapter12.2 for guidance.

We are not recruiting participants who cannot understand English.

c) What steps are you taking to determine that potential participants are competent to participate in the decision-making process? If your study may enroll adults who are unable to consent, describe (i) how you will assess the capacity to consent, (ii) what provisions will be taken if the participant regains the capacity to consent,(iii) who will be used as a legally authorized representative, and (iv) what provisions will be made for the assent of the participant.

Participants will be reading the consent form before beginning the screener. Participants must be English literate to participate as the questionnaires, consent forms, and Woebot app are only available in English. The participant will have to select "Agree" to participate in the study. Contact information is also provided during consent for the participant to use if they have questions about the study.

14. Assent Background (less than 18 years of age)

Title : Woebot for Substance Use Disorders during COVID-19 (SU sIRB)
Approval Period: 04/30/2022 - 04/30/2023

15. HIPAA Background

15.1 Waiver of Authorization for **waiver of authorization for recruitment** Recruitment

a) **Describe the protected health information (PHI) needed to conduct screening or recruitment. PHI is health information linked to HIPAA identifiers. List BOTH health information AND HIPAA identifiers. If you are using STARR, use the Data Privacy Attestation to ensure that your request will match your IRB-approved protocol.**

The following PHI will be collected via online screening through REDCap or Qualtrics. PHI collected: name, phone number, email address, date of birth, gender/biological sex, substance use, health, demographic information, zipcode, IP address (auto collected by Qualtrics), geographic location (auto collected by Qualtrics).

b) Please Answer:

Y **Do you certify that the use or disclosure of protected health information involves no more than a minimal risk to the privacy of individuals?**

Y **Do you certify that the research could not practically be conducted without the waiver?**

Y **Do you certify that you have adequate written assurances that the protected health information will not be reused or disclosed to any other person or entity, except as required by law, for authorized oversight of the research project, or for other research for which the use or disclosure of protected health information would be permitted?**

Y **Do you certify that the research could not practically be conducted without access to and use of the protected health information?**

c) **Please describe an adequate plan to protect any identifiers from improper use and disclosure.**

Data that is obtained from the Qualtrics or REDCap assessments will be stored and protected within Qualtrics or REDCap. Data that is obtained via Woebot will be encrypted and stored on Amazon Web Services (AWS); Woebot Labs data gathering and storage procedures are compliant with both the Health Insurance Portability and Accountability Act (HIPAA) and the European Union's General Data Protection Regulation (GDPR) compliant. Only members of the research team (PI, Co-PIs, biostatistician, research assistant) will have access to the data. Each participant will be assigned a unique study ID number that will take the place of any identifying information. Surveys will be done online with individual survey URLs matched to study ID provided to participants. All data therefore will be coded for the large dataset. No names will be attached to surveys. Study staff is responsible for the coding. De-identified data may be sent by secure email settings provided by Stanford. Woebot user data provided to Stanford will be de-identified and linked via study ID to the study assessments we collect via REDCap or Qualtrics and the data will not be shared outside of the Woebot and Stanford teams. The PD and co-investigator and the research team will have access to the study data. All data will be locked or password-protected or both. The codes of names and ID numbers will be accessed by the research team only, stored securely in Qualtrics or REDCap. The research staff will all be HIPAA and CITI trained and compliant and supervised by [name].

d) **Please describe an adequate plan to destroy the identifiers at the earliest opportunity consistent with conduct of the research, unless there is a health or research justification for retaining the identifiers or such retention is otherwise required by law.**

The identifiers in the research will be destroyed following publication of the main manuscript.

Title : Woebot for Substance Use Disorders during COVID-19 (SU sIRB)
Approval Period: 04/30/2022 - 04/30/2023

16. Attachments

Attachment Name	Attached Date	Attached By	Submitted Date
Woebot Recruitment Flyer	04/27/2020	[name]	
Woebot for Substance Use Disorders - Possible Subreddits	04/27/2020	[name]	
Woebot Branching Logic	04/27/2020	[name]	
Referrals for Substance Use Treatment 12.9.19	04/27/2020	[name]	
Directions installing registering Woebot App	04/27/2020	[name]	
Woebot Crisis Language Response	04/27/2020	[name]	
[name]'s CITI Completion Report	04/27/2020	[name]	

Woebot for Substance Use Disorders During COVID-19

NCT04460027

October 01, 2021

Statistical Analysis Plan

Paired samples t-tests and chi-square tests compared the groups on baseline variables. EOT survey completion was 84% (152/180) and significantly higher for participants identifying as non-Hispanic white (89%) compared to other racial/ethnic groups (74%) and for participants with a college degree (89%) relative to high school degree (74%) (p-values<.01). Retention also was higher for participants who at baseline reported more pandemic-related mental health effects and lower levels of craving, pain, and pain interference (p-values<.05). Of the 17 treatment participants lost to follow-up, 16 never registered with the W-SUDs app. Fig. 1 shows rates of noncompliance by condition. Two participants randomized to waitlist (2%) downloaded Woebot (not SUD-tailored) from the app store during the study period. Analyses followed the intent-to-treat protocol.

General Linear Models (multivariate models) tested for group differences in changes in the primary outcome and secondary outcomes. The dependent variables were baseline to EOT change scores. The models adjusted for baseline group differences and applied weights to adjust for correlates of study retention. Participant weights were calculated as the inverse of predicted probability values from a logistic regression model predicting EOT retention with race/ethnicity, education, craving, pain intensity, and pandemic-related mental health effects. Pain rating and pain interference were highly correlated ($r = .74$), due to missing data and multicollinearity, the pain rating item was not included. To examine associations among outcomes, bivariate correlations were run for the changes scores. Lastly, survey data were linked to treatment participants' app use metrics and tested for associations.

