Updated consent forms and HIPAA authorization will be uploaded before the start of recruitment. Ads, questionnaires, etc. will be uploaded for review before recruitment begins.

Recruitment will be a joint effort by Stanford University and Woebot Labs. Woebot will communicate the research opportunity through social media channels. The Stanford team will recruit through listservs and contact participants from previous research studies who are interested in future studies. Working with [name] research team at Stanford, the Woebot team will take part in mapping out message development for the intervention and Woebot's IT team will lead the app programming (including build and quality control/de-bugging). Woebot will collect user data via the Woebot app (automatic process), which

Title : Woebot for Substance Use Disorders during COVID-19 (SU sIRB)
Approval Period: 04/30/2022 - 04/30/2023

will be provided to the Stanford team. The Woebot team will participate in disseminating the study findings via publications and presentations. Participants from recruitment channels will go through and eligibility screener and if eligible, will be asked to use the W-SUDS for 8 weeks and answer a couple of questionnaires administered at the beginning and end of the 8 week period. The data from the questionnaires and app usage during the 8-week period will be analyzed to inform the next study. Woebot will rely on Stanford University IRB for review of this study.

The Stanford team will lead the study evaluations including the study measures, data collection (baseline and follow-ups at the 4- and 8- week marks), data analyses, and writing up of study findings for dissemination. Participants will be randomized to condition after completion via the online assessment platform, which has the functionality to allow randomization to one of two webpages. Those randomized to W-SUDs or WL will see a private, study-only Woebot website or the WL website, respectively. Only then will participants randomized to W-SUDs be informed of Woebot in order to avoid contamination. The WL group has no intervention during the 8-week period and the team will monitor for any intervention usage.

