a) State the following: (i) the number of participants expected to be enrolled at Stanford-affiliated site(s); (ii) the total number of participants expected to enroll at all sites; (iii) the type of participants (i.e. students, patients with certain cancer, patients with certain cardiac condition) and the reasons for using such participants.

May 2021: N=160 was proposed for study enrollment. Final enrollment was N=180. Qualtrics panel recruitment was the main recruitment method and had resulted in n=160; n=20 were from other recruitment sources described in the protocol. For the next study, we'll try Qualtrics recruitment before other sources, as the Qualtrics panel requires a prepaid agreement and results in speedy recruitment.

N=160 (nationally) will be invited to participate in this study and entered into the study on a rolling basis.

Title : Woebot for Substance Use Disorders during COVID-19 (SU sIRB)
Approval Period: 04/30/2022 - 04/30/2023

Recruitment will be a joint effort by Stanford University and Woebot Labs. Neither election or declining to participate in the study will impact Woebot users ability to continue using the product as they wish. Inclusion criteria include: all genders aged 18-65 years, access to Woebot on smartphone, be available and committed to engage with app and complete assessments, be willing to provide email address (to distribute incentives), and be literate in English (as W-SUDs conversational and video materials will be in English). Exclusion criteria include: pregnancy (as W-SUDs will not be specifically developed to address the unique needs of this population), history of severe drug/alcohol use, opioid misuse without medication-assisted treatment, and suicide attempt or opioid overdose within the past year. Randomization will occur through the survey program by the time the participant finishes the baseline survey.

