Participants and Recruitment: N=160 (nationally) will be invited to participate in this study. Recruitment channels may include Woebot Labs' social media avenues (e.g., Facebook, Twitter, LinkedIn, Woebot.io, Nextdoor), Craigslist, Reddit, physical flyers, emailing clinics (with their permission), posting to Stanford Staffers listserv, and advertising to the WELL cohort. Stanford staff may post in other listservs with permission, and contact participants from other studies if those participants have interest in other studies. The team may use Qualtrics panels to recruit. Participants will be entered into the study on a rolling basis. Neither election or declining to participate in the study will impact Woebot users ability to continue using the product as they wish. Inclusion criteria include: all genders aged 18-65 years, access to Woebot on smartphone, be available and committed to engage with app and complete assessments, be willing to provide email address (as this is how assessment incentives will be distributed), and be literate in English (as W-SUDs conversational and video materials will be in English).

Exclusion criteria include: pregnancy (as W-SUDs will not be specifically developed to address the unique needs of this population), history of severe drug/alcohol use, opioid misuse without medication-assisted treatment, and suicide attempt or opioid overdose within the past year. Participants residing outside the U.S. will not be included. Participants who have ever used Woebot will also not be recruited. Use of Woebot (without SUDs program) post randomization, regardless of group assignment, is allowed. Those who elect to participate will be provided with a specific code to enter into Woebot to cue the SUDs specific content.

Randomization: Randomized controlled trial of W-SUDs vs a wait-list control condition (will get access to the SUD program at the end of the study; no intervention during the 8 week period)

This supplemental study proposes to randomize individuals to two conditions (estimating n=80 in each group), W-SUDs or a wait-list control condition, in order to:

- (i) compare between group substance use outcomes at end-of-treatment;
- (ii) assess and analyze comparative impact of Covid-19 in each group;
- (iii) conduct a moderation analysis. Do putative moderators moderate treatment impact upon substance use outcomes?

Primary aim / outcome: Compare between group treatment outcomes.

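### The SAP names a paired-samples t-test to compare two unmatched randomised arms at baseline; the wording needs correcting, and the covariates of the outcome models need naming

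*SAP*

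**What the plan says.** The first sentence of the SAP's analysis text describes the baseline comparison: "Paired samples t-tests and chi-square tests compared the groups on baseline variables". Its second paragraph describes the outcome models. On the dependent variable it says "The dependent variables were baseline to EOT change scores", and on adjustment "The models adjusted for baseline group differences and applied weights to adjust for correlates of study retention". The SAP names the predictors of the retention-weight model one by one. It names no covariates for the outcome models and gives no rule for deciding what counts as a baseline group difference.

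The protocol describes a parallel-group design. Section 8a, under Randomization, states: "This supplemental study proposes to randomize individuals to two conditions (estimating n=80 in each group), W-SUDs or a wait-list control condition". Section 2a says allocation is done by the online assessment platform, "which has the functionality to allow randomization to one of two webpages". Section 8a adds that "Randomization will occur through the survey program by the time the participant finishes the baseline survey" and, on accrual, that "Final enrollment was N=180". Neither document gives the number in each arm, and neither mentions matching, pair-randomisation or crossover.

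**The concern.** A paired t-test is computed on differences within linked pairs of values. Here each arm is a separate set of people seen at one time point, so nothing links a given W-SUDs participant to a given wait-list participant. Any pairing would come from the order of rows in the data file.

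Two things are at stake. The baseline table may rest on a test that does not fit the comparison. In addition, the SAP goes on to adjust for baseline group differences and offers no other account of how those were identified. If the tests did pick the covariates, then whether a borderline continuous variable enters the primary model could turn on file order.

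**Working it through.** The SAP gives no baseline p-value, standard deviation or arm size, so there is no figure of its own to reproduce. The check sets the stated test against the design and then measures how much the difference matters.

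**1. Design against test.** Rolling entry, individual allocation by the survey platform and two separate conditions make independent groups. The SAP sentence compares the groups on baseline variables, so it cannot be read as a test of within-person change. The chi-square tests in the same sentence suit independent groups, so the error concerns continuous variables only.

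**2. Unequal arms.** With, say, 88 and 92 people, a paired test is undefined unless some are dropped. If allocation was simple randomisation (an assumption; the documents do not say), the number in one arm is Binomial(180, 0.5). The chance of unequal arms is then 1 − P(90) = 0.94, and the mean gap is 10.7 people. The SAP's own figures do not settle the split: two wait-list participants reported as 2% fits any wait-list arm of 80 to 133 people.

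**3. Equal arms: overall behaviour.** Assume 90 per arm. The independent-samples test has df = 178 and critical value 1.973; the paired test has df = 89 and critical value 1.987. With arbitrary pairing of unrelated people:

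| | Paired | Independent |
|---|---|---|
| Type I error (20,000 simulations) | 4.9% | 4.8% |
| Power at d = 0.3 | 51.2% | 51.7% |
| Power at d = 0.5 | 91.3% | 91.6% |

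**4. Equal arms: dependence on row order.** With equal standard deviations, t(paired) = t(independent) / √(1 − r), where r is the chance correlation produced by the row order. Under random ordering r has mean 0 and standard deviation 1/√(n − 1) = 1/√89 = 0.106, so its central 95% range is about ±0.208.

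For t(independent) = 2.0 (p = 0.047):
- r = +0.208: t = 2.0/√0.792 = 2.247, paired p = 0.027
- r = −0.208: t = 2.0/√1.208 = 1.820, paired p = 0.072

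The paired test reaches 5% when r > 1 − (t/1.987)²:

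| Independent t | Independent p | r needed | Share of orderings with paired p < 0.05 (formula) | Same share (simulation) |
|---|---|---|---|---|
| 2.00 | 0.047 | −0.013 | 55% | 55% |
| 1.97 | 0.050 | 0.017 | 44% | 43% |
| 1.90 | 0.059 | 0.086 | 21% | 21% |

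The simulation used 60 data sets with 400 orderings each and agrees with the formula. The effect is confined to borderline variables: at t = 1.5 the formula gives a share near 0, and at t = 2.5 a share near 100%.

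**5. Link to the outcome models.** The SAP puts baseline tests in one paragraph and adjustment for baseline group differences in the next. It states no p-value threshold and does not say that the tests selected the covariates. The protocol's Data Analysis text (section 8a) describes effect sizes and gives no adjusted model. The baseline tests are thus the only candidate source in the documents, but the link is not written down.

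**The case against.** The strongest reply is that this is a slip of the pen for independent samples. The documents cannot show which test was run. If the arms were unequal, a paired test would have had to drop people, which makes a wording error more plausible, though it does not prove one. If it was a slip, no result changes. This stands, and it is why confirmation comes before any rerun.

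It can also be said that the harm is small even if a paired test was used. That stands too: with equal arms the error rate is kept and power falls by half a percentage point or less at the two effect sizes shown.

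A reader might go further and infer that the paired tests decided which covariates entered the primary model, so that the adjusted treatment estimate rests on an arbitrary pairing. The documents do not support stating this. The SAP never says that covariates were chosen by these tests or by any p-value. Nothing here carries a changed covariate through to the treatment estimate. Nor should the general weakness of baseline significance testing, which produces chance differences under any valid test, be charged to the paired test. That weakness bears on the covariate list and is a separate point.

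Finally, a covariate list written now would not be truly pre-specified, because the SAP already reports retention results. This is correct, and the list must say so.

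**Conclusion.** The concern holds in a limited form. As written, the SAP names the wrong test for comparing continuous baseline variables between two unmatched arms, and nothing elsewhere in the documents corrects it. The categorical comparisons are unaffected.

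The size depends on facts the documents do not give. With unequal arms the stated test cannot use all participants. With 90 per arm its overall properties match the correct test closely, and the defect is that a borderline p-value moves with row order. A route from these tests to the outcome-model covariates is a reasonable inference because no other is offered, but it is not a stated rule, and no bias in the treatment estimate has been shown. The firmer gap is that the adjusted primary analysis cannot be reconstructed from the SAP, since its covariates are unnamed. The figures rest on 90 per arm, equal standard deviations in the formula, and simple randomisation for the chance of unequal arms.

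**What to change.** 1. In the baseline sentence, replace the paired-samples t-test with the independent-samples t-test.
2. Check the analysis code and state which test was run. If it was the independent-samples test, correcting the sentence is enough. If paired tests were used, rerun the baseline table and any outcome model whose covariates change as a result.
3. Name the covariates of every outcome model in a list that does not depend on baseline p-values. Label the list as fixed after data were seen, and report the model already run beside it.

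Cost: one or two sentences, a check of the code, the listed-covariate models wherever they differ from those already run, and possibly a rerun of the baseline table. No new data are needed.
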